#### 2.2.4 Analysis visits

All assessments (except safety assessments in the roll-over phase), including unscheduled assessments, will be allocated to analysis windows. Tables, listings and figures will present the analysis windows as defined below, not the CRF visits.

Allocation of assessments will be done using their relative day in the phase (ADYP) (see section 2.2.3) according to the following table:

Phase	Analysis window	Target ADYP	Lower limit ADYP	Upper limit ADYP
Roll-Over	Baseline a	-	-	-
	Week 4	29	1 [c]	43
	Week 8	57	44	71
	Week $(8 + x^{b} * 4)$	$57 + (x^{b*28})$	$44 + (x^{b*28})$	$71 + (x^{b*28})$
	Week 52	365	352	End day of phase
Treatment	Baseline a	-	-	-
	Week 1	8	1°	11
	Week 2	15	12	18
	Week 3	22	19	25
	Week $(3+x^b)$	$22 + (x^{b*7} \text{ days})$	$19 + (x^{b*7} \text{ days})$	$25 + (x^{b*7} days)$

#### Table 3: Analysis visits

Document template OTH.STAT.010 v3

Page 21 of 84

System Version: 1.0, Status: Approved, Document ID: VV-TMF-172580

SGS Statistical Analysis Plan				
ARGX-113-1905		Final	analysis	Final 1.0 of 26APR2024
	Week 51	358	355	361
	Week 52	365	362	End day of phase
Follow-up	FU Week 4	28	1	42
	FU Week 8	56	43	End day of phase

a Baseline is the assessment at the roll-over visit, so no analysis visit windows are required for this time point. For participants with a roll-over phase, the baseline analysis visit will be assigned to the roll-over phase and will not be repeated in the treatment phase. For participants without a roll-over phase, the baseline analysis visit will be assigned to the treatment phase.

b x=1,..., 10 for roll-over phase, x=1,...,.47 for treatment phase

An assessment at the roll-over visit will be attributed to Baseline in case it is before the first IMP administration, to Week 1 otherwise.

Baseline is defined in section 2.2.2.

For the analysis of ECG, a 12-weekly allocation will be used, as defined in Table 4.

Phase	Analysis window	Target ADYP	Lower limit ADYP	Upper limit ADYP
Treatment	Baseline a	-	-	-
	Week 12	85	1 a	127
	Week 24	169	128	211
	Week 36	253	212	295
	Week 48	337	296	361
	Week 52	365	362	End day of phase
Follow-up	FU Week 4	28	1	42
	FU Week 8	56	43	End day of phase

Table 4: Analysis visits for ECG

a Baseline is the assessment at the roll-over visit, so no analysis visit windows are required for this time point.

x=1 through the maximum number of 12-weeks periods on treatment for any participant minus 2

For GTI wider windows are used:

- Week 26 (wide range): from ADY=145 until ADY=221 with target on ADY=183
- Week 52 (wide range): from ADY=327 until ADY= end of treatment phase with target on ADY=365
- Other assessments will be allocated as in table 3 but will not be presented in the tables (only in listings).
- Additional visit window: Endpoint: last record post baseline.

_	SGS	Statistical Analysis Plan	
AF	GX-113-1905	Final analysis	Final 1.0 of 26APR2024

Analysis of ABQOL and EQ-5D-5L will be done on following visits:

- Roll-over (per CRF visit)
- At CRmin (assessment done within 28 days after achieving CRmin)
- At start of new treatment period
- At EoT/ET (per CRF visit)

Additionally, assessments for PDAI, PD, albumin and LDL-C are also allocated to analysis visits based on AWADY using start of subperiod as reference day, as shown in Table 5. Assessments for PK will only be allocated to analysis visits based on Table 5.

Phase/ Period	Subperiod	Analysis window	Target AWADY	Lower limit AWADY	Upper limit AWADY
Roll-over	Off- treatment RO	Baseline d	-	-	-
		Week 4	29	1	43
		Week 8	57	44	71
		Week (8+ x b *4)	$57 + (x^{b*28})$	$44 + (x^{b*28})$	$71 + (x^{b*28})$
		Week 52	365	352	End day of phase
Treatment /Treatment period n	On- treatment n	TPnB	1	-INF	1ª
		Week 1	8	1 a	11
		Week 2	15	12	18
		Week 3	22	19	25
		Week $(3+x^b)$	$\begin{array}{l} 22 + (x^{b*7} \\ days) \end{array}$	19 + (x b *7 days)	$\begin{array}{c} 25 + (x^{b} * 7 \\ days) \end{array}$
		Week 52	365	362	End day of Or treatment n subperiod
	Off- treatment n	Week 1	8	1	11
		Week 2	15	12	18
		Week 3	22	19	25

Table 5: Additional analysis visits for PDAI, PD, PK, Albumin and LDL-C

Document template OTH.STAT.010 v3

Page 23 of 84

CONFIDENTIAL AND PROPRIETARY

System Version: 1.0, Status: Approved, Document ID: VV-TMF-172580

SGS	Statistical A	nalysis Plan		
ARGX-113-1905	Final ar	•		inal 1.0 of 26APR2024
	Week (3+ x b )	22 + (x b *7 days)	19 + (x b *7 days)	$\begin{array}{c} 25 + (x^{b*7} \\ days) \end{array}$
	Week 52	365	362	End day of Off-treatment n subperiod

a An assessment on Day 1 will be attributed to TPnB in case it is before the first IMP administration, to Week 1 otherwise.

b x=1,...,10 for roll-over phase, x=1,...,48 for treatment phase

c Upper limit of last analysis window in roll-over phase cannot exceed first IMP administration date.

d Baseline is the assessment at the roll-over visit, so no analysis visit windows are required for this time point.

For those participants who will start a new treatment period, the last assessment in a period, prior to the administration of the new period, will be allocated to the appropriate visit within this previous period and will also be allocated as the treatment period baseline (TPnB) visit of the new period.

Per parameter and analysis window, the value closest to the target ADY/AWADY will be used in analysis tables and figures, other values will only be listed. If more than one value is located at the same distance from the target, then the latest in time will be selected. The value latest in time will be identified using, in order of preference, the assessment date/time, the visit label or the group identifier (if applicable). For immunogenicity assessments, values resulting in an unevaluable ADA/NAb status are given the lowest priority when the selection is made. For other assessments, missing values are removed before the selection is made.

Partially missing assessment dates disabling allocation to analysis windows will not be imputed and thus these assessments will not be considered in the per-timepoint analysis. Note that these assessments are included in analyses on worst-case.

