1.2. Schema

Figure 1: ARGX-113-1905 Trial Design

CR=complete clinical remission; CRmin=complete remission on minimal therapy; CRoff=complete remission off therapy; DC=disease control; Efg=efgartigimod PH20 SC; EoT=end of treatment; FU=follow-up; SC=subcutaneous; Trt Fail=treatment failure; W=week

Table 1:Schedule of Activities for ARGX-113-1905 for Participants in CR, CR on Minimal Therapy, and CR
off Therapy at Rollover From ARGX-113-1904

Trial period		Open-label extension														Follo	w-up
Visit number	V1 Roll over ^a	V1 + 4 weeks	V1 + 8 weeks	V1 + 12 weeks	V1 + 16 weeks	V1 + 20 weeks	V1 +24 weeks	V1 + 28 weeks	V1 + 32 weeks	V1 + 36 weeks	V1 + 40 weeks	V1 + 44 weeks	V1 + 48 weeks	V1 +51 weeks EoT/ET	UNS ^b	Safety follow- up 1 EoT/ET + 4 weeks ^c	Safety follow- up 2 EoT/ET + 8 weeks EoS ^c
Assessment/procedure	±0 days						±2 d	ays ^d								±3 days ^d	±3 days ^d
Informed consent	Х																
Inclusion/exclusion criteria	Х																
Weight ^e	Х						Xe							Х			
ECG ^{f,g}	Х			X			Х			Х			Х	Х		Х	Х
Physical examination and vital signs ^{f,h}	X	Х	X	Х	Х	Х	Х	Х	Х	Х	Х	X	Х	Х	Х	Х	Х
Urinalysis ^{f,i}	Х	Х	Х	Х	Х	Х	Х	Х	Х	Х	Х	Х	Х	Х	Xb	Х	Х
Urine pregnancy test ^{f,j}	Х	Х	Х	Х	Х	Х	Х	Х	Х	Х	Х	Х	Х	Х	Xb	Х	Х
Vaccination antibodies ^f	Х	Х	Х	Х	Х	Х	Х	Х	Х	Х	Х	Х	Х	Х	Xb	Х	Х
Blood sampling																	
 clinical chemistry and hematology^{f,k} 	X	Х	X	X	Х	Х	Х	Х	Х	Х	Х	X	Х	Х	Xb	X	Х
• anti-Dsg-1 and anti- Dsg-3 antibodies	Х	X	X	Х	Х	Х	Х	Х	Х	Х	X	X	Х	Х	Xb	Х	Х

Trial period		Open-label extension														Follo	ow-up
Visit number	V1 Roll over ^a	V1 + 4 weeks	V1 + 8 weeks	V1 + 12 weeks	V1 + 16 weeks	V1 + 20 weeks	V1 +24 weeks	V1 + 28 weeks	V1 + 32 weeks	V1 + 36 weeks	V1 + 40 weeks	V1 + 44 weeks	V1 + 48 weeks	V1 +51 weeks EoT/ET	UNSb	Safety follow- up 1 EoT/ET + 4 weeks ^c	Safety follow- up 2 EoT/ET + 8 weeks EoS ^c
Assessment/procedure	±0 days						±2 d	lays ^d								±3 days ^d	±3 days ^d
• PK ¹	Х	X	X	Х	X	X	X	Х	X	X	X	X	Х	Х	X ^{b,m}	Х	Х
 Total IgG and IgG subtypes^{f,l} 	X	X	Х	X	Х	X	Х	X	Х	Х	Х	Х	Х	Х	Xb	X	Х
• immunogenicity ^{f,n}	X	X	X	Х	Х	Х	Х	X	Х	Х	Х	X	Х	Х		Х	Х
 IgG autoantibody subtypes and specificity^f 	X	X	Х	х	Х	Х	Х	x	Х	х	Х	Х	Х	Х	Xb	Х	Х
PDAI ^f	X	X	X	X	Х	Х	Х	X	Х	Х	Х	X	Х	X	X	X	X
ABQOL ^{f,o}	Х				at (CRmin	(or the	next or	i-site vi	sit)				Х			
EQ-5D-5L ^{f,o}	Х				at (CRmin	(or the	next or	i-site vi	sit)				Х			
Disease assessment ^{f,p}	Х	Х	X	Х	Х	Х	Х	Х	Х	Х	Х	Х	Х	Х	Х	Х	Х
Lymphocyte populations (at selected sites) ^q	X			X			Х				Х			Х		Х	Х

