- ^b In case of suspected new lesions as reported by the participants, AEs, flare, or other safety reasons, participants should come to the clinic. This may require an unscheduled visit. Depending on the reason for the visit, different assessments need to be performed. Refer to Section 8 for more information. Participants with new lesions or flare after achieving CR should return to weekly on-site visits. Participants with flare who had achieved CRmin or CRoff should switch to the visit schedule outlined in Table 2.
- ^c Follow-up 1 will be the EoS visit for participants who ended treatment before W49 or 4 weeks before ET. Both follow-up visits will be required only for participants who continue to receive efgartigimod PH20 SC for at least 1 visit between W49 and W52 or during the last 4 weeks before ET.

^d Study visit windows are ± 2 days during the treatment period and ± 3 days for the follow-up visits.

^e Weight will be measured and BMI will be calculated accordingly, at the rollover visit, at W26 (or the next on-site visit if W26 does not coincide with an on-site visit) and W52. Weight will also be measured if there has been an obvious change since the last measurement.

^f Assessment or procedure will be completed predose at visits when IMP is administered.

^g The ECG will be recorded at baseline, every 3 months while receiving efgartigimod PH20 SC treatment, at CRmin (or the next on-site visit if CRmin is achieved during a week without an on-site visit), and at EoS. The ECG (heart rate, PR, QT, and QRS interval) will be read centrally, and QTcF and QTcB will be calculated. The ECG will be recorded only at baseline and EoS in participants not receiving efgartigimod. Additional ECGs may be performed at the discretion of the investigator during unscheduled visits.

- ^h A complete physical examination will be performed at each on-site visit. Vital sign measurements include systolic and diastolic blood pressure, heart rate, and body temperature.
- ⁱ Urinalysis will be performed by dipstick method and will include specific gravity, pH, protein, glucose, ketones, blood, bilirubin, urobilinogen, nitrite, leukocyte esterase, and microscopic examination (if blood or protein is abnormal).
- ^j A urine pregnancy test will be performed locally and at least once every 4 weeks.

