ABQOL=Autoimmune Bullous Disease Quality of Life; AE=adverse event; ALT=alanine aminotransferase; ALP=alkaline phosphatase; AST=aspartate aminotransferase; BMI=body mass index; BUN=blood urea nitrogen; CR=complete clinical remission; CRmin=CR on minimal therapy; CRP=C-reactive protein; DC=disease control; Dsg=desmoglein; ECG=electrocardiogram; EoC=end of consolidation; EoS=end of study; EoT=end of treatment; EQ-5D-5L=EuroQol 5-dimension 5-level scale; ET=early termination; GGT=gamma-glutamyl transferase; GTI=Glucocorticoid Toxicity Index; IgG=immunoglobulin type G; IMP=investigational medicinal product; LDH=lactate dehydrogenase; MCV=mean corpuscular volume; NAb=neutralizing antibody; PD=pharmacodynamic; PDAI=Pemphigus Disease Area Index; PK=pharmacokinetics; QTcF=Fridericia corrected QT interval; rHuPH20=recombinant human hyaluronidase PH20; RBC=red blood cells; SC=subcutaneous(ly); UNS=unscheduled visit; V=visit at site; V1 + 7x=visit 1 + 7 times x with 'x' being the weeks post V1 (eg, V1 + 7x3 is the visit at W3 [21 days post visit 1]); W=week; WBC=white blood cells

^a For participants who roll over from ARGX-113-1904 to ARGX-113-1905, the baseline visit will occur at the EoS/ED visit of ARGX-113-1904. All assessments are performed before IMP administration.

^b A minimum of 6 on-site visits (rollover (V1) to W6 or start of retreatment +5 weeks) is required before switching to home administrations, even if CR is reported earlier.

^c Home visits are allowed once a participant achieves CR but not before W7 or not before the start of retreatment +6 weeks. The investigator should call the participant every 2 weeks until CRmin to confirm the participant is still in CR and to determine the prednisone tapering schedule.

^d In case of suspected new lesions as reported by the participant, AEs, flare, or other safety reasons, the participant should come to the clinic. This may require an unscheduled visit. Depending on the reason for the visit, different assessments need to be performed. Refer to Section 8 for more information.

^e Follow-up 1 will be the EoS visit for participants who ended treatment before W49, or 4 weeks before ET. Both follow-up visits will be required only for participants who continue to receive efgartigimod PH20 SC for at least 1 visit between W49 and W52, or during the last 4 weeks before ET.

^f Study visit windows are ± 2 days during the treatment period and ± 3 days for the follow-up visits.

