#### 2.2.5 Worst-case

[figure not shown]
A worst-case analysis visit will be created for the combined treatment and follow-up phase for parameters for which abnormalities and/or toxicity grades are defined to summarize values considered as the worst-case over time. For abnormalities, this visit is derived per parameter and in case both the lowest and the highest values are considered abnormal, a participant can have two worst-case analysis visits for a same parameter. For toxicity grades, the worst-case is the value associated to the highest toxicity grade and is derived per parameter and toxicity direction (hypo/hyper).

All non-missing post-baseline values in the treatment and follow-up phase, including unscheduled assessments, will be considered when deriving the worst-case analysis visit.

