#### 5.4.3 Presentation of results

Uncorrected QT interval will only be listed, RR interval will not be displayed.

Continuous ECG parameters will be summarized by means of descriptive statistics at each analysis visit. Actual values and changes from baseline will be shown in the same table.

Abnormalities of the actual values will be presented as cross-tabulations of the abnormality at each post-baseline analysis visit, and at the worst-case analysis visit

SGS	Statistical Analysis Plan	
ARGX-113-1905	Final analysis	Final 1.0 of 26APR2024

versus the baseline abnormality. This table will also show numbers and cumulative numbers (QTcF and QTcB only) of participants with treatment-emergent abnormalities (see Definition of terms). The denominator for the percentage is the total number of participants per treatment and per analysis visit in the Safety analysis set.

Abnormalities of the QTcF and QTcB changes from baseline will be presented as a tabulation of the change from baseline abnormality at each post-baseline analysis visit and at the worst-case analysis visit. This table will also show cumulative numbers over decreasing change from baseline abnormalities of participants. The denominator for the percentage is the total number of participants per treatment and per analysis visit in the Safety analysis set.

Tables to be produced for the topline results (see list of outputs in section 8.1) will show data for PV+PF participants as well as for PV participants.

All ECG data will be listed, but only for participants with any post-baseline abnormality or clinically significant value or change.

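### SAP Table 4 places the V1+48-week ECG and the on-time V1+51-week end-of-treatment ECG in the same window, so the end-of-treatment ECG drops out of the by-visit ECG tables

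*SAP*

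**What the plan says.** **Windows.** SAP 2.2.4 gives ECG its own windows: "For the analysis of ECG, a 12-weekly allocation will be used, as defined in Table 4". SAP Table 4 sets Week 48 at target day 337, range 296–361, and Week 52 at target day 365, from day 362 to the end of the phase. Where several values share a window, "the value closest to the target ADY/AWADY will be used in analysis tables and figures, other values will only be listed".

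**Schedule.** The ECG row of Protocol Table 1 (Section 1.3, repeated in SAP 9.3.1) is marked at V1+48 weeks and again in the column headed "V1 +51 weeks EoT/ET". The visit window is ±2 days. Footnote g adds: "The ECG will be recorded only at baseline and EoS in participants not receiving efgartigimod".

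**What else is kept.** SAP 2.2.5: "All non-missing post-baseline values in the treatment and follow-up phase, including unscheduled assessments, will be considered when deriving the worst-case analysis visit". SAP 5.4.3: "All ECG data will be listed, but only for participants with any post-baseline abnormality or clinically significant value or change".

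**Week numbering.** Protocol Table 1 heads the end-of-treatment column V1+51 weeks, but its footnotes speak of W52. Protocol Table 2 supports two readings. Its abbreviation note says "V1 + 7x3 is the visit at W3 [21 days post visit 1", which makes W52 equal to V1+52 weeks. Its footnote b says "A minimum of 6 on-site visits (rollover (V1) to W6 or start of retreatment +5 weeks) is required", which makes W6 equal to start +5 weeks and so W52 equal to V1+51 weeks.

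**The concern.** Two ECGs scheduled three weeks apart share one analysis window, and only one can be tabulated. The other is the last scheduled on-treatment ECG. Nothing else can fill the Week 52 row: SAP Table 1 ends the treatment phase at the end-of-treatment visit, and later ECGs go to the follow-up rows.

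ECG is part of the primary safety endpoint. SAP 5.4.3 specifies the descriptive statistics, the abnormality cross-tabulations and the QTcF/QTcB change table by analysis visit. The participants concerned are still being dosed at weeks 48–51 after starting at roll-over, so they are among those with the longest exposure in this trial.

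**Working it through.** **Inputs**

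| Item | Value | Source |
|---|---|---|
| ECG targets | days 85, 169, 253, 337, 365 | SAP Table 4 |
| Upper bounds of Weeks 12, 24, 36, 48 | 127, 211, 295, 361 | SAP Table 4 |
| Day count | first day of phase = day 1 | SAP 2.2.2 |
| Start of treatment phase | earlier of consent and roll-over, for participants not in CRmin or CRoff | SAP Table 1 |
| Scheduled ECGs | V1+48 weeks and V1+51 weeks, ±2 days | Protocol Table 1 |

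**Step 1: reproduce the SAP's figures.** Target day = 7 × week + 1. Weeks 12, 24, 36, 48 and 52 give 85, 169, 253, 337 and 365, as stated. Midpoints of adjacent targets:

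- (85 + 169)/2 = 127, as stated
- (169 + 253)/2 = 211, as stated
- (253 + 337)/2 = 295, as stated
- (337 + 365)/2 = 351, but the SAP has 361

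The value 361 is the upper bound of the Week 51 row in SAP Table 3, where the midpoint is (358 + 365)/2 = 361.5. SAP Table 4 has no Week 51 row.

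**Step 2: place the scheduled ECGs** (consent on the roll-over day, as Protocol Table 1 schedules it).

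| Visit | Day | Allowed days | Current window | Distance from Week 48 target |
|---|---|---|---|---|
| V1+48 weeks | 7 × 48 + 1 = 337 | 335–339 | Week 48 | 0–2 |
| V1+51 weeks | 7 × 51 + 1 = 358 | 356–360 | Week 48 | 19–23 |
| V1+52 weeks | 7 × 52 + 1 = 365 | 363–367 | Week 52 | – |

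**Step 3: apply the selection rule.** Five possible days for each of the first two visits give 5 × 5 = 25 pairings. Both ECGs fall in Week 48 in all 25, and the V1+48 ECG is selected in all 25. If the V1+48 ECG is missing, the end-of-treatment ECG is tabulated but labelled Week 48.

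**Step 4: when the end-of-treatment ECG would reach Week 52.** A visit due on day 358 must be 362 − 358 = 4 days late, which is outside ±2. Consent k days before roll-over adds k to the day count. An ECG 358 days into the schedule then needs k ≥ 4; one taken at the early limit (356) needs k ≥ 6, and one at the late limit (360) needs k ≥ 2.

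**Step 5: test the bounds 351/352.** Days 335–339 go to Week 48. Days 356–360 and 363–367 go to Week 52. The end-of-treatment ECG is dropped in 0 of 25 pairings. Because 339 + 12 = 351, the V1+48 ECG stays in Week 48 even if consent preceded roll-over by up to 12 days.

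**The case against.** **The affected group may be small.** Dosing stops at CRmin, and footnote g then limits ECGs to baseline and end of study. Participants on Protocol Table 1 who are dosed from roll-over enter already in CR. On an uninterrupted taper from 0.5 mg/kg under Protocol 6.5.1, CRmin takes about 2 + (2 to 4) + 3 + 8 = 15 to 17 weeks. A collision needs almost a year of dosing without CRmin. This stands as a limit on reach. The 25 pairings count calendar days, not participants.

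**Safety information is largely preserved.** The end-of-treatment ECG is eligible for the worst-case rows of the abnormality and QTc tables, and it is listed for anyone with a flagged post-baseline finding. An ECG from three weeks earlier is still tabulated, and no hypothesis is tested. This stands too, with two qualifications. A worst-case row shows the value only if it is the extreme one, and the descriptive summary is specified only by analysis visit. For a participant with no flagged finding, the ECG is therefore neither in that summary nor listed.

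**The cut matches other tables.** The SAP states no midpoint rule, and treatment-phase Week 52 starts at day 362 in SAP Tables 3 and 5 as well. Labs and vital signs from an on-time V1+51 visit also leave Week 52 empty. But there the value keeps its own Week 51 row (days 355–361), whereas SAP Table 4 merges it with another scheduled visit. The SAP's 4-weekly roll-over rows start Week 52 at day 352. They do not govern ECG, because safety assessments in that phase are not windowed, so they serve only as a precedent.

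**Footnote g does not name an end-of-treatment ECG.** True; the point relies on the grid, which marks one. The treatment-phase Week 52 row in SAP Table 4 also anticipates an ECG at about that time.

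**Conclusion.** The concern holds. For a Protocol Table 1 participant dosed from roll-over and still on efgartigimod at weeks 48–51, with both ECGs done on time, the end-of-treatment ECG is always excluded from the by-visit rows and Week 52 has no value. This assumes that the grid governs over footnote g and that consent is given on the roll-over day or too few days earlier to move the ECG past day 361.

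The documents do not allow a count of those affected. Participants off efgartigimod are outside the point, as are those whose dosing follows a roll-over phase, because their day count restarts. Protocol Table 2 participants are affected only if W52 means V1+51 weeks and they also have an ECG nearer day 337; if W52 means V1+52 weeks (day 365), they are not.

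The consequence is an incomplete by-visit display of a primary safety measure. The window should be corrected, but the worst-case analysis is not compromised.

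**What to change.** In SAP Table 4, end Week 48 at day 351 and start Week 52 at day 352. This works under either reading of W52. State in the SAP which protocol week Week 52 represents.

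The cost is two numbers in one table. The side effect is that an ECG from the V1+51 visit would be labelled Week 52 while labs and vital signs from the same visit are labelled Week 51 under SAP Table 3; a footnote can explain this.

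An alternative is to assign the end-of-treatment ECG by CRF visit, as SAP 2.2.4 already does for ABQOL and EQ-5D-5L. That avoids the label mismatch, but it mixes early terminations into the same row and departs from the SAP's general use of analysis windows.

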Participants or their caregivers (a person of legal age that the participant proposes to perform the administrations) may also self-administer efgartigimod PH20 SC after they have successfully completed self-administration training (in ARGX-113-1904 with at least 1 refresher training in ARGX-113-1905 or during ARGX-113-1905). All participants and/or their caregivers will receive a home guide for transport, storage, preparation, and administration of the IMP.

At any postbaseline visit before DC is achieved, the prednisone dose will be adjusted by incrementing dosage according to clinical judgment, with the recommendation to increase by 1 or more steps (Table 4) in case of disease progression or insufficient clinical change. To facilitate common judgments among investigators, recommendations for assessment of disease progression and insufficient clinical change are:

- Disease progression: increase of at least 5 in PDAI activity score compared to baseline score, observed at any postbaseline visit before DC
- Insufficient clinical change: the absence of DC after 3 to 4 weeks of the participant being treated at the starting baseline prednisone dose or after 3 to 4 weeks of any new incremented dose of prednisone

The recommendations of the prednisone dose escalation are:

- Stepwise escalation of daily prednisone dose by 1 or more steps according to clinical judgment in case of disease progression
- Adjustment by incrementing dosage by 1 step in case of insufficient clinical change
- Possible further escalation from the previous step by 1 or more steps, according to clinical judgment and under the same recommendation as above
- Maximum escalation to 1.5 mg/kg qd for 3 weeks

If DC is not attained after a minimum of 3 weeks of the participant receiving oral prednisone 1.5 mg/kg qd, then the participant will be considered a treatment failure and will be withdrawn from the trial.

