- The C-GTI, which serves as a primary instrument intended to capture common glucocorticoid toxicities (ie, toxicities that are likely due to glucocorticoid exposure and sensitive to cumulative doses over the period of 6 months to 3 years), has 9 functional domains (specifically: BMI, glucose control, blood pressure, lipid metabolism, bone mineral density, muscle strength, skin toxicity, neuropsychiatric effects, and infection). Each of the domains contains 3 to 4 weighted items that correspond to varying degrees of glucocorticoid toxicity within their respective domain. Among the 9 GTI domains, bone mineral density is excluded if the GTI will be measured at intervals shorter than 1 year, because bone densitometry is not sufficiently reliable in measuring changes at shorter intervals. Therefore, in the context of the ARGX-113-1904 trial with a maximum duration of 30 weeks, the index is truncated by removing the "bone mineral density" domain. Development of the GTI beyond the original validation work has suggested 2 approaches to analysis. These approaches provide complementary information about the ability of an investigational agent to reduce GC toxicity and also optimize the granularity with which the GTI captures the GC toxicity. The CWS is designed to assess cumulative GC toxicity, regardless of whether the toxicity has lasting effects or is transient. New toxicities that occur are added, but toxicities that appear to resolve on follow-up are not removed. Thus, the CWS serves as a lasting record of GC toxicity observed, and can only increase or remain the same over time. In the case of the presence of some GC toxicity at baseline, the AIS can be used to establish that a new therapy is effective at diminishing any baseline GC toxicity over time. With the AIS, toxicities can be removed if improvement occurs, and added if worsening occurs. If toxicities present at baseline or occurring during the trial resolve over the course of follow-up, then that improvement is reflected in a negative score for that item during the interval. Both the CWS and the AIS are calculated for each interval, and then the interval scores are summed.

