period (W52) and overall (Endpoint). The last post-baseline assessment (Endpoint) is considered as the overall CWS/AIS and is calculated as a cumulative score over all post-baseline timepoints. Details on calculation of CWS/AIS are provided in appendix 9.1. The complementary GTI specific list (GTI-SL) will only be listed.

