#### 4.1.3.6 OTHER EFFICACY ENDPOINTS

Descriptive statistics will be provided for the number of flares. Tables will be provided for PV participants and all participants (PV+PF), overall and by disease status at roll-over.

SGS	Statistical Analysis Plan	
ARGX-113-1905	Final analysis	Final 1.0 of 26APR2024

Frequency tabulations will be provided for the percentages of treatment failure (with 95% exact confidence interval) and its different reasons, overall and by disease status at roll-over.

PDAI activity subscores (mucosal, skin and scalp), PDAI activity score and PDAI total score will be summarized by means of descriptive statistics at each analysis visit. Actual values, changes from baseline and percent changes from baseline will be tabulated by analysis visits overall. Additionally, changes and percent changes versus 1904 baseline will be tabulated by analysis visits overall. Furthermore, actual values, changes from TPnB and percent changes from TPnB will be tabulated by analysis visits by period/subperiod. Tables to be provided for PV participants and for all participants (PV+PF).

Frequency tabulations will be provided for the percentages of participants within each outcome of QoL questionnaire items (ABQOL and EQ-5D-5L) at each analysis visit. Additionally, cumulative percentages (starting with the best outcome result) will be calculated. Descriptive statistics will be provided for the total ABQOL score and for the EQ-5D-5L VAS score.

Descriptive statistics will be provided for the C-GTI scores AIS and CWS. C-GTI will be analysed on complete cases: i.e. participants with C-GTI at baseline and at least one post-baseline visit. Participants where first post-baseline GTI improvements/worsening have not been obtained with respect to the baseline moment but with respect to a later moment (i.e. no GTI assessment at baseline visit) are excluded from analyses and are only listed.

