## 9.1.2 CWS and AIS calculation

## 9.1.2.1 CWS

The CWS is calculated as the sum of the worsening items: i.e. with weights >0. For the items with subitems, i.e. skin toxicity and neuropsychiatric effects, only the subitem with the highest positive weight is used. As an example, if neither insomnia nor depression were present at the start of the GTI interval but there is mild insomnia and moderate depression present at post-baseline, then only the moderate depression is used for the neuropsychiatric weight (+74 points).

In the CWS calculation, the most severe infection in every GTI interval is scored (so in case of 2 periods, the score for an infection is counted twice for the overall CWS at endpoint).

CWS is calculated at W26 and at W52 as the sum of the worsening items in all postbaseline timepoints up to that timepoint respectively. The overall CWS at endpoint is the sum of all worsening items over all post-baseline timepoints.

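### The overall (Endpoint) C-GTI row pools last cumulative scores over unequal follow-up, so it understates full-follow-up CWS for participants who withdraw early

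*SAP*

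**What the plan says.** SAP 2.2.4 sets two wide GTI windows: Week 26 (days 145 to 221) and Week 52 (day 327 to the end of the treatment phase). Records outside them go to listings only. It then adds "Additional visit window: Endpoint: last record post baseline". SAP 4.1.2.6 gives this record its meaning: "The last post-baseline assessment (Endpoint) is considered as the overall CWS/AIS and is calculated as a cumulative score over all post-baseline timepoints". Appendix 9.1.2.1 repeats it for CWS: "The overall CWS at endpoint is the sum of all worsening items over all post-baseline timepoints". On infection the same appendix notes "so in case of 2 periods, the score for an infection is counted twice for the overall CWS at endpoint".

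SAP 4.1.3.6 limits the analysis to "participants with C-GTI at baseline and at least one post-baseline visit". SAP 4.1.2.6 has GTI collected at baseline, Week 26 and Week 52/EoT/ET. Planned Table 14.2.1.8.1 shows Week 26, Week 52 and Overall.

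Protocol 8.3.10 says of CWS that it "can only increase or remain the same over time". Protocol 1.1 (repeated in 4.1) says that if disease control (DC) is not reached after at least 3 weeks on 1.5 mg/kg prednisone, "then the participant will be considered a treatment failure and will be withdrawn from the trial".

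**The concern.** The Overall row has no common time base. A participant whose only post-baseline GTI is an ET record a few weeks after roll-over contributes one short interval. A completer contributes about 52 weeks, usually in two intervals. The two are averaged as if they measured the same thing.

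Follow-up is also partly determined by outcome, because failure to reach DC leads to withdrawal. C-GTI is the only endpoint that Protocol Section 3 lists for the objective on the health impact of glucocorticoids, and the table shows the two ARGX-113-1904 arms side by side. If one arm has more early withdrawal, the Overall row can show a toxicity difference that is only a difference in follow-up. Elsewhere the SAP does allow for time: prednisone is normalised per day (3.4.2) and adverse events per participant-year (5.1.2). Nothing comparable is planned for C-GTI.

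**Working it through.** The documents give no expected CWS, withdrawal rate or power for this endpoint, so there is no planned figure to reproduce. The check has three parts.

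**1. Scoring rules (SAP 9.1).** The largest possible CWS in one interval is 36 (BMI) + 44 (glucose) + 44 (blood pressure) + 30 (lipids) + 63 (myopathy) + 26 (skin) + 74 (neuropsychiatric) + 93 (infection) = 410, whatever the interval's length. Infection alone can give 93 with one interval and 2 × 93 = 186 with two. Worsening points are added and never removed, so assessments after an ET record could leave that participant's CWS unchanged or raise it. Endpoint CWS is therefore at or below full-follow-up CWS. Missing items score 0 (9.1.1), which adds no points for unseen worsening. AIS can move either way, so the same argument gives it no direction.

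**2. Windows.** An ET record before day 145 (144/7 = 20.6 weeks) is in neither visit window and is tabulated only under Endpoint. An ET record on days 222 to 326 is also in neither, but that participant should normally have a Week 26 record and so appear in the Week 26 row.

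No-DC withdrawal can come early. Participants entering without DC start at 1.5 mg/kg/day, so the 3-week minimum can be met from about week 3. For someone starting at 0.5 mg/kg and moving one step every 3 to 4 weeks, the four steps below 1.5 mg/kg take 12 to 16 weeks. Adding 3 weeks at 1.5 mg/kg gives 15 to 19 weeks.

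**3. Illustration of size (every input is an assumption).** Let completers' mean Week 52 CWS be C = 100, d the share withdrawing early, t the week of withdrawal and r their accrual rate relative to completers, with linear accrual.

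- Early score = C × r × t/52
- Endpoint mean = (1 − d)C + d × C × r × t/52
- Full-follow-up mean = (1 − d)C + d × C × r

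| d | t | r | Early score | Endpoint mean | Full-follow-up mean | Shortfall | Endpoint minus completers |
|---|---|---|---|---|---|---|---|
| 10% | 20 | 1 | 38 | 93.8 | 100 | 6.2% | −6.2 |
| 20% | 8 | 2 | 31 | 86.2 | 120 | 28.2% | −13.8 |
| 30% | 8 | 3 | 46 | 83.8 | 160 | 47.6% | −16.2 |
| 20% | 20 | 3 | 115 | 103.1 | 140 | 26.4% | +3.1 |

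The shortfall against full follow-up is present in every row. The comparison with completers changes sign at r = 52/t: 6.5 at week 8, 4.3 at week 12, 2.6 at week 20 and 2.0 at week 26.

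For the arm comparison, take r = 1 and t = 8, with 10% withdrawing in one arm and 20% in the other. The Overall means differ by (0.20 − 0.10) × 100 × (1 − 8/52) = 8.5 points with identical accrual.

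**The case against.** The strongest reply is that the consequence is small. No hypothesis is tested (Protocol 9.2), comparisons of prior arms are purely descriptive (9.1.1), and Table 14.2.1.8.1 is not a topline table. Week 26 and Week 52 rows stand beside Overall, C-GTI is listed by participant, and steroid burden is also visible through normalised cumulative prednisone dose and prednisone-related adverse events. This limits the problem to one row and sets its weight. It does not give that row a common time base.

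It can also be said that some early withdrawals will never enter. The ET visit is held if possible (Protocol 7.2), and the schedule footnotes name only visit 1, W26 and W52 for GTI, although the schedule column is headed EoT/ET and SAP 4.1.2.6 includes ET. A participant without a post-baseline GTI is excluded, not counted low. That stands, and it makes the number affected uncertain.

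A reader might infer that early withdrawals are mostly treatment failures on the highest prednisone dose. The documents do not show this. They give no frequencies, and Protocol 7.2 expects withdrawal at the participant's request or the investigator's discretion to be uncommon. The no-DC rule does not reach participants who enter with DC already achieved, unless they later flare after CRmin and start a new cycle. Withdrawal for flare before CRmin need not be at the maximum dose.

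A reader might also infer that early scores are low and must pull the row below completers. The weights are steps, for example 93 for a grade 3 infection and 74 for a moderate neuropsychiatric change, and each can be scored in full in a short interval.

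**Conclusion.** The point holds in this form. The Overall C-GTI row mixes unequal and partly outcome-dependent follow-up without adjustment, and for CWS it can only understate, or at best match, the full-follow-up score of participants who withdraw early with an ET GTI. This rests on the SAP's scoring rule and the protocol's statement that CWS does not fall; it needs no numerical assumption.

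The size does need assumptions. The 6% to 48% range comes from assumed withdrawal shares of 10% to 30%, withdrawal at week 8 or 20, rate ratios of 1 to 3 and linear accrual. The direction relative to completers depends on timing and toxicity rate, which the documents do not give, and the direction for AIS is undetermined. It would also be too strong to say that early terminators appear only under Endpoint: that is true of ET records before day 145, but those leaving on days 222 to 326 normally also appear at Week 26. This is a worthwhile, cheap improvement to a descriptive secondary table; no error rate or power is affected.

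**What to change.** In SAP 2.2.4, SAP 4.1.2.6 and Table 14.2.1.8.1, present Endpoint separately for participants whose last GTI is in the Week 52 window and for those whose last GTI is earlier. For each group and each ARGX-113-1904 arm, show the number of participants, days from roll-over to last GTI and number of GTI intervals. Do not present the pooled row alone as the overall result.

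Do not replace this with a rate such as score × 182/days. One grade 3 infection in a participant whose last GTI is on day 42 would become 93 × 182/42 = 403, close to the 410 maximum for an interval.

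Also reconcile the Week 52 score. SAP 4.1.2.6 describes it as covering the last 26-week period, whereas 9.1.2 makes it cumulative from baseline. Until one is chosen, the Week 52 row cannot serve as the comparator for Overall.

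The cost is SAP wording and a few extra rows in one table. The downside is smaller groups per row, and the group with full follow-up will largely repeat the Week 52 row if that row is cumulative.
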